### **Efficacy Analysis**

The efficacy data will be descriptively summarized with the mITT and PP analysis populations and presented by study part and treatment group. Data for the Group 3 dose in both study parts will be pooled and summarized as well.

The mITT analysis will be considered primary and the PP supportive.

For all analyses of BCVA data, missing data will be imputed using multiple imputation methods. Patients who receive rescue medication/procedures within 6 months after the study treatment is initiated will be considered failure to achieve a gain of at least 15 BCVA letters. For continuous measures, all data points after a subject starts rescue medication will be replaced with the last observation prior to rescue medication administration.

Sensitivity analyses on the primary endpoint will be performed as follows:

- 1) On observed data only, with subjects requiring rescue medications prior to Month 6 included as treatment failures (mITT and PP populations)
- 2) Imputing missing data using the last observation carried forward, with subjects requiring rescue medications prior to Month 6 included as treatment failures (mITT population)
- 3) On observed data only, with subjects who require rescue medications prior to Month 6 using their Month 6 data (mITT population)

The same approach to missing data as described for BCVA data will apply to CST data.

The time to achieve a treatment response of gain of 15 or more letters from baseline BCVA will be analyzed using the Kaplan-Meier method. Survival plots will be created and the survival time will be presented as mean, median, 95% confidence intervals (CIs) for the median, and the range.

Change from baseline in number of letters read correctly (using BCVA) and change from baseline of retinal CST (by using SD-OCT scan) in the study eye during the 12-month period will be summarized by treatment groups at scheduled visits. Additionally, 95% CIs for the treatment estimates in changes from baseline will be constructed.

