## Summary of Known and Potential Risks and Benefits to Human Subjects

ProDex is developed to provide an ideal, safe, long-acting, DSP delivery system for the treatment of macular edema.

Subjects receiving ProDex IVT injection may be at risk for transient vitreous opacity, which might result in transient visual acuity decrease but would be expected to resolve within 2-6 weeks after study drug dosing. IVT injections have been associated with endophthalmitis, eye inflammation, increased IOP, vitreous hemorrhage, and retinal detachments. Subjects should be monitored following the injection. Use of corticosteroids may produce posterior subcapsular cataracts, increased IOP, glaucoma, and may enhance the establishment of secondary ocular infections due to bacteria, fungi, or viruses.

From the experience of preclinical and preliminary clinical data, the expected adverse reactions of ProDex IVT injection on subject with macular edema following CRVO and BRVO include vitreous opacity, increased IOP, visual acuity decrease, conjunctival hemorrhage, eye pain, dry eye, foreign body sensation, conjunctival hyperemia, cataract, floaters, and hypertension. Previous human experience from Ozurdex shows that potential adverse reactions include vitreous detachment, optic nerve damage, visual acuity and field defects, posterior subscapular cataract formation, secondary ocular infection, and perforation of the globe where there is thinning of the cornea or sclera. The expected systemic adverse reactions such as hypertension, hyperglycemia, vasovagal reaction, and facial flushing are also rare, but will be monitored carefully.

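### Change in BCVA and CST is frozen at the last pre-rescue value through Month 12, and no analysis with different rescue handling is planned for these endpoints

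*Combined protocol and SAP*

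**What the plan says.** All of the relevant rules are in the Efficacy Analysis section of the synopsis.

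- **Binary endpoint.** The rule begins "Patients who receive rescue medication/procedures within 6 months after the study treatment is initiated will be considered failure to achieve a gain of at least"; the threshold it goes on to name is the 15-letter one.
- **Continuous measures.** "all data points after a subject starts rescue medication will be replaced with the last observation prior to rescue medication administration". The rule names no last visit, and change in BCVA and CST is summarised at scheduled visits over the 12-month period.
- **Missing data.** "For all analyses of BCVA data, missing data will be imputed using multiple imputation methods", and "The same approach to missing data as described for BCVA data will apply to CST data".
- **Sensitivity analyses.** The list opens with "Sensitivity analyses on the primary endpoint will be performed as follows". Its third item is "On observed data only, with subjects who require rescue medications prior to Month 6 using their Month 6 data (mITT population").
- **Intervals.** For the continuous endpoints, "95% CIs for the treatment estimates in changes from baseline will be constructed".

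The Interim Analysis section adds that evaluation after Month 6 is exploratory, that no formal comparisons between groups will be made, and that Part 1 data are unmasked as of protocol v4.

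**The concern.** Carrying one pre-rescue reading to every later visit turns a by-visit mean into a mixture. Subjects without rescue contribute their value at that visit, observed or multiply imputed. Rescued subjects contribute a value from whichever earlier visit preceded rescue. Two groups with the same underlying course can then show different Month 6 or Month 12 means only because rescue came at different times. A carried value also enters the CI with the same standing as a reading taken that day.

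The plan recognises this for the binary endpoint, where analysis 3 uses rescued subjects' own Month 6 data. Change in BCVA and CST has no counterpart. Reducing retinal thickness is a stated secondary objective, and CST change is the first secondary measure listed. With no formal comparisons planned, readers will judge the strengths largely from these means and intervals, in groups of 10 to 15 subjects (about 26 for pooled Group 3).

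**Working it through.** The plan states no figure that depends on the rescue rule, so there is none to reproduce. The check has a textual part and an illustrative part.

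**1. Rescue handling, endpoint by endpoint**

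| Endpoint | Planned handling | Alternative rescue handling |
|---|---|---|
| 15-letter gain at Month 6 | Rescued = failure | Analysis 3: own Month 6 data |
| Change in BCVA by visit | Last pre-rescue value carried | None |
| Change in CST by visit | Last pre-rescue value carried | None |

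Sensitivity analyses 1 and 2 keep the failure rule and vary only the missing-data method. The sentence extending the BCVA approach to CST follows the list, so its reach is slightly unclear. Read plainly, it concerns missing data and does not extend the list to CST. CST change is in any case a continuous measure, so the carry-forward rule covers it.

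**2. How timing enters**

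The visit schedule puts Visit 6 at Day 60, Visit 11 at Day 270 and Visit 12 at Day 360. A subject rescued just after Visit 6 contributes the Day 60 reading at Visits 7 to 12, which is 12 − 6 = 6 visits. A subject rescued just after Visit 11 contributes a carried reading at 12 − 11 = 1 visit.

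**3. Shift relative to the as-observed mean**

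Let p be the share of the group rescued by that visit and g the average of (as-observed minus carried value) among those rescued. Then

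carried mean − as-observed mean = −p × g.

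Neither p nor g is in the documents. With assumed values, the size of the shift is:

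| p | g = 5 letters | g = 10 letters | g = 100 µm (CST) |
|---|---|---|---|
| 10% | 0.5 | 1.0 | 10 µm |
| 30% | 1.5 | 3.0 | 30 µm |
| 50% | 2.5 | 5.0 | 50 µm |
| 70% | 3.5 | 7.0 | 70 µm |

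Per subject, a 10-letter gap in one rescued person moves the mean by 10/10 = 1.0 letter in a Part 1 group of 10, and by 10/15 = 0.7 letters in a Part 2 group of 15.

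**4. The sign is not fixed**

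Compare instead with the mean that would have been seen without rescue. Assume that mean change peaks at +7 letters and fades to +1 by Month 12. If rescue is unrelated to acuity and the carried reading sits at the peak, the carried mean is too high by p × (7 − 1): 0.3 × 6 = 1.8 letters at 30% rescued. If low readings prompt rescue, the shift can go the other way. A simulation on such a path (200,000 subjects, rescue at −5 letters or worse, 37–60% rescued) gave Month 12 shifts from +0.5 to −3.3 letters. With rescue timing unrelated to acuity it gave +1.4 to +2.5.

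**5. Confidence intervals**

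Assume Month 12 change with mean 5 and SD 15 letters, correlation 0.7 between carried and as-observed values, and carried values 10 letters lower on average. Coverage of the as-observed mean by the nominal 95% t-interval (20,000 runs) was:

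| p | n = 15 | n = 26 (pooled Group 3) |
|---|---|---|
| 10% | 94.7% | 94.0% |
| 30% | 89.5% | 84.7% |
| 50% | 79.4% | 66.0% |
| 70% | 63.4% | 41.2% |

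With a 5-letter gap and n = 15, coverage was 94.8%, 93.8%, 90.7% and 87.0%. The loss comes from the shifted mean. At n = 15 and a 10-letter gap the average half-width stays between 8.3 and 8.6 letters whatever the share rescued, so the interval itself gives no warning.

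**The case against.** Freezing at the last pre-rescue value is a defensible way to keep the effect of rescue out of a summary of a single injection, and an as-observed summary mixes that effect back in. The study is exploratory and has no formal sample size, formal comparisons are ruled out, and the Part 1 dose has already been chosen. All of this stands. It argues for keeping the planned analysis and for modest weight. It does not explain why the binary endpoint has a second view of rescue and the continuous ones have none. The freeze also operates before Month 6, so the exploratory label on later data does not remove the issue.

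A reader might infer more than the text supports:

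- **That nothing else is planned for the continuous endpoints.** Per-protocol summaries, pooled Group 3 and RVO-type subgroups for selected secondary endpoints are planned. None is stated to change the rescue rule.
- **That the means rest on frozen values.** Only rescued subjects contribute one.
- **That post-rescue data enter no summary.** Analysis 3 uses them at Month 6, and the text does not clearly exclude them from the proportions with BCVA above 73 letters or CST below 300 µm.
- **That the carried value is typically a trough.** No rescue criteria, timing or rate are given. The risk summary mentions "transient vitreous opacity, which might result in transient visual acuity decrease but would be expected to resolve within 2-6 weeks after study drug dosing", but does not link this to rescue, and it gives no reason for CST to be biased.

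Collection of post-rescue data can be inferred only for BCVA at Month 6, from analysis 3. For CST, and for visits after Month 6, it is an assumption.

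**Conclusion.** The point holds in this form: change in BCVA and CST is carried forward from the last pre-rescue visit through Month 12, and no analysis of these endpoints handles rescue differently. For rescued subjects the by-visit means therefore depend on rescue timing, and the CIs treat a carried value as measured.

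Direction and size cannot be established from the documents. On the assumptions shown, the effect is minor if about 10% are rescued (1 letter for a 10-letter gap, coverage close to nominal) and material if half are (5 letters, coverage 79.4% at n = 15). These figures illustrate the mechanism; they do not predict this trial's results. This is a descriptive and estimand weakness in secondary endpoints. It leaves the primary endpoint untouched and is worth correcting because the remedy is cheap.

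**What to change.** Keep the planned analysis. For change in BCVA and in CST at each scheduled visit, pre-specify before Part 2 is unmasked:

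1. A companion summary of all observed values regardless of rescue, mirroring sensitivity analysis 3, with the number of subjects rescued by that visit shown for each group. This is the minimum.
2. Where group size allows, a version with post-rescue values set to missing and multiply imputed, so that the CI reflects that they are unknown. The Efficacy Analysis section does not specify the imputation model, so it should be written down.

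Part 1 data are already unmasked, so label both analyses post hoc there.

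The cost is SAP wording and extra tables, with no new data provided post-rescue visits are recorded. The first analysis includes the effect of rescue and should say so. The second may be unstable in groups of 10 to 15, especially if many subjects are rescued. The versions may differ visibly, and the text should say in advance what each one estimates.

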#### **Subgroup Analysis**

Subgroup analyses will be performed for the primary efficacy endpoint and selected

secondary endpoints by RVO type.

### Safety Analysis

All safety data analyses will be performed on the safety population and displayed in subject data listings and summarized in tables. Treatment-emergent adverse events (TEAEs) will be listed and categorized by start date, stop date, seriousness, severity, relationship to IP, action taken, and outcome. TEAEs with a missing relationship to study treatment will assume greatest relationship to study treatment. TEAEs with missing severity grades will be categorized as "missing" for tabulation of TEAEs by severity. Summary tables will display the total number of TEAEs and the number of subjects with each TEAE by treatment groups. TEAEs will be summarized by the Medical Dictionary for Regulatory Activities (MedDRA) system organ class and preferred term for all TEAEs, serious adverse events (SAEs), and TEAEs leading to study withdrawal. In addition, TEAEs will be summarized by day of onset relative to the injection day of IP.

Safety data including physical examination, vital signs, clinical laboratory data, IOP assessments, SLB, indirect ophthalmology, FA, and FP evaluations will be descriptively summarized by treatment group.

Continuous safety data will be summarized by visit and include changes from baseline. Continuous data will also be converted to categorical values where possible (ie, below, within, and above normal ranges) and summarized in shift from baseline tables. Categorical safety data collected by visit will be summarized showing the counts and percentages in each category at each visit, as well as shifts from baseline.

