**Exclusion Criteria:** 

- 10. History of ocular hypertension, glaucoma, or optic nerve head change consistent with glaucomatous damage in the study eye.
- Active ocular hypertension (with or without treatment) ≥ 22 mm Hg in the study eye at the Screening or Day 1 visit.
- 12. Aphakia or presence of anterior chamber intraocular lens in the study eye.
- 13. Active retinal neovascularization in the study eye.
- 14. Active or history of choroidal neovascularization in the study eye.
- 15. History of central serous chorioretinopathy in either eye.
- 16. Presence of rubeosis iridis in the study eye.
- 17. Any active ocular infection (ie, bacterial, viral, parasitic, or fungal) in either eye at the Screening Visit or on Day 1.
- 18. History of herpetic ocular infection in the study eye or adnexa.
- 19. Presence of active or inactive toxoplasmosis in either eye at the Screening Visit or on Day 1.
- 20. Presence of visible significant scleral thinning or ectasia in the study eye that would preclude safe IVT injection.
- 21. Media opacity in the study eye that precludes clinical and photographic evaluation (including but not limited to preretinal or vitreous hemorrhage, lens opacity).
- 22. Cataract surgery in the study eye within 3 months, or other intraocular surgery in the study eye within 6 months prior to the Screening Visit; or these surgeries are planned during the course of the study.
- 23. Anticipated need for ocular surgery in the study eye during the 12-month study period.
- 24. History of pars plana vitrectomy, radial optic neurotomy, or sheathotomy in the study eye.
- 25. Use of hemodilution for the treatment of RVO within 3 months prior to the Screening Visit.
- 26. Use of IVT ranibizumab or bevacizumab in the study eye within 6 weeks prior to the Screening Visit; or IVT aflibercept in the study eye within 8 weeks prior to the Screening Visit.
- 27. Use of laser of any type in the study eye within 3 months prior to the Screening Visit.
- 28. Previous use of non-depot IVT steroids in the

study eye within 3 months prior to the Screening Visit.

- 29. IVT Ozurdex in the study eye within 6 months prior to the Screening Visit.
- 30. Any prior use of Retisert or Iluvien in the study eye.
- 31. Use of systemic steroids or heparin within 1 month prior to the Screening Visit; or anticipated use at any time during the study.

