### **Analysis Population**

The populations for analysis applied in this study are defined as follows:

*Safety population*: All randomized subjects who receive any dose of study drug administration.

*Modified intent-to-treat (mITT) population*: A subset of the safety population comprised of subjects who have at least 1 post-treatment efficacy evaluation. *Per protocol (PP) population*: A subset of the mITT population comprised of subjects who complete the study without any major protocol violations.

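### The cataract percentage is taken over all dosed subjects, including those whose study eye already has an artificial lens, so it understates the risk in eyes that can develop cataract

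*Combined protocol and SAP*

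**What the plan says.** The Safety Analysis section of the Synopsis sets one population for all safety work: "All safety data analyses will be performed on the safety population and displayed in subject data listings and summarized in tables". The Analysis Population section defines it as "All randomized subjects who receive any dose of study drug administration". Lens status plays no part in that definition.

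For adverse events the plan says "Summary tables will display the total number of TEAEs and the number of subjects with each TEAE by treatment groups", and that "TEAEs will be summarized by the Medical Dictionary for Regulatory Activities (MedDRA) system organ class and preferred term for all TEAEs", with the same layout for serious events and for events leading to withdrawal. A table by day of onset is added. Each event is to be "categorized by start date, stop date, seriousness, severity, relationship to IP, action taken, and outcome"; eye is not in that list. The only planned subgroup analysis is of efficacy, by RVO type.

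On the lens, exclusion criterion 12 removes "Aphakia or presence of anterior chamber intraocular lens in the study eye", and criterion 22 removes cataract surgery in the study eye that is planned or took place in the 3 months before screening. A posterior chamber lens from older surgery is not excluded.

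On risk, the summary of risks and benefits states: "Use of corticosteroids may produce posterior subcapsular cataracts, increased IOP, glaucoma". It also lists cataract among the reactions expected from this product.

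**The concern.** A study eye whose natural lens has been removed is not at risk of cataract. Each such subject adds one to the denominator and can add nothing to the study-eye numerator. The tabulated cataract percentage then answers a different question from the one a reader will bring to it, namely how often a treated eye that can develop cataract does so.

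This matters because cataract is one of the product's own expected reactions, safety by strength is a secondary objective, and the trial is descriptive. With no formal comparisons planned, the tabulated percentages are themselves the safety result. Part 2 sets Group 3 beside a larger volume of the same formulation, so ocular safety by group will be read closely.

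A smaller matter goes with it. Only the study eye is injected, and the efficacy endpoints are all defined for that eye, but the safety section does not say how events in the other eye will be shown.

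**Working it through.** The plan states no cataract rate, phakic count or fellow-eye rate, so there is no figure of its own to reproduce.

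**Inputs from the documents.** Denominator: all randomized and dosed subjects (Analysis Population; Safety Analysis). Group sizes: 10, 10 and 11 in Part 1, and up to 30 subjects randomized 1:1 in Part 2, so up to 15 per group (Sample Size Calculation; Synopsis).

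**Assumptions.** Pseudophakic share of study eyes, *s*: 0% to 50%. Cataract risk in phakic treated eyes, *r*: 20% to 40%. Fellow-eye cataract rate, *q*: 0% to 15%. None of these is in the documents.

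**Step 1, dilution.** Pseudophakic eyes contribute no cataract, so the reported study-eye rate is *r* × (1 − *s*).

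| *r* | *s* = 0% | 10% | 20% | 30% | 40% | 50% |
|---|---|---|---|---|---|---|
| 20% | 20% | 18% | 16% | 14% | 12% | 10% |
| 30% | 30% | 27% | 24% | 21% | 18% | 15% |
| 40% | 40% | 36% | 32% | 28% | 24% | 20% |

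**Step 2, one Part 2 group of 15 with three study-eye cataracts** (exact 95% intervals):

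- All subjects: 3/15 = 20.0% (4.3% to 48.1%).
- *s* = 20%, 12 phakic: 3/12 = 25.0% (5.5% to 57.2%).
- *s* = 1/3, 10 phakic: 3/10 = 30.0% (6.7% to 65.2%).
- *s* = 40%, 9 phakic: 3/9 = 33.3% (7.5% to 70.1%).

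**Step 3, lens mix between groups.** With binomial lens status in two groups of 15, the chance that the groups differ by at least 3 pseudophakic eyes is 25%, 32% and 35% at *s* = 20%, 30% and 40%. As an unfavourable case, take 6 versus 2 pseudophakic eyes and an equal phakic risk of 30%. The expected table rates are 0.30 × 9/15 = 18% and 0.30 × 13/15 = 26%. In subjects this is 0.30 × 9 = 2.7 against 0.30 × 13 = 3.9, a gap of 1.2.

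**Step 4, whether the better denominator would settle a dose question.** With 9 and 13 phakic eyes at 30% risk, the standard deviation of the difference is √(0.30 × 0.70/9 + 0.30 × 0.70/13) = √(0.0233 + 0.0162) ≈ 0.20, or 20 points. It would not.

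**Step 5, only if both eyes shared one row.** With independent eyes, the subject-level rate is 1 − (1 − *r*(1 − *s*))(1 − *q*). At *r* = 30% and *s* = 0%, values of *q* of 5%, 10% and 15% give 33.5%, 37.0% and 40.5%. At *r* = 30%, *s* = 40% and *q* = 15% the result is 1 − 0.82 × 0.85 = 30.3%, close to the phakic risk only because two distortions cancel.

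**The case against.** **The size is assumed.** This stands. If no pseudophakic subject is enrolled there is no dilution, and the documents do not say how many are.

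**The study is exploratory and small.** This also stands. No formal comparison is planned, the intervals in Step 2 overlap almost entirely, and with 31 plus up to 30 subjects each cataract can be read in the listings. It limits what can be gained, but it does not make the all-subject denominator the right one for a lens event.

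**Other displays may show lens change.** Slit lamp findings are to be summarized by group with shifts from baseline. The section specifies neither lens grading nor eye for them, so this is a partial answer at best.

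**A reader might infer that eyes are pooled and that fellow-eye events are charged to the dose.** The documents do not support that. The safety section never says eyes will be pooled; it is silent. Relationship to study drug is listed for each event, all data go into subject listings, and a table of all events counts them whatever their cause. Two things make the silence worth resolving: no table restricted to related events is named, and "TEAEs with a missing relationship to study treatment will assume greatest relationship to study treatment", with no exception for the uninjected eye. Nor is fellow-eye information lost, since a summary table does not remove listed data. The fellow eye is in any case an imperfect background, because it need not have RVO or meet the study-eye criteria.

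**A reader might infer that lens imbalance will produce a false dose difference.** The 6 versus 2 split is a chosen case. Given 8 pseudophakic eyes among 30 subjects, a split at least that uneven has a chance of about 21%, and its effect is about one subject. The chance variation in Step 4 is much larger than the 8 points it creates.

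**Conclusion.** The concern holds for the cataract denominator. It follows from the stated population and the eligibility criteria, and its direction is certain for study-eye events: the percentage is too low by the factor (1 − pseudophakic share). At an assumed share of 20% to 40%, three cataracts in 15 read as 20% where the phakic-eye figure is 25% to 33%. At a share of zero the two agree.

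The question of eye is an omission to be clarified, not an error shown in the text. If fellow-eye events did enter the same row, they would push the rate the other way, so no net direction can be claimed for a both-eyes table.

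The gain is a more accurate cataract rate. It is not the ability to detect a difference between Groups 3 and 4, which these group sizes cannot give under either denominator.

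**What to change.** In the Safety Analysis section and the table shells:

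1. Report cataract events and slit lamp lens worsening as study eyes affected over study eyes phakic at baseline, by treatment group.
2. Show baseline lens status of the study eye by treatment group.
3. State that ocular events are tabulated separately for study eye and fellow eye, with non-ocular events in their own table.
4. Keep the all-subject table by system organ class and preferred term as the overall display.

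The cost is analysis wording and a few tables. Lens status has to be checked for criterion 12, and slit lamp examination is already a safety measure; the sponsor should confirm that baseline lens status and the eye affected by each event are recorded in usable form. The downside is a smaller denominator, wider intervals and a less favourable cataract percentage. No test, endpoint or sample size changes.

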- 8. Presence of an epiretinal membrane in the study eye which, in the opinion of masked Evaluating Investigator, is the primary cause of macular edema, or is severe enough to prevent gain in visual acuity despite reduction in macular edema.
- History of clinically significant (CS) intraocular pressure (IOP) elevation (ie, a rise of ≥10 mm Hg or an absolute IOP ≥ 25 mm Hg which required treatment) in response to topical or systemic steroid treatment in either eye.

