# Safety Measures:

TLC399 (ProDex)	Taiwan Liposome Company, Ltd.
Clinical Trial Protocol: TLC399A2002	12 October 2018, v5.0

observations, mean, standard deviation, median, minimum, and maximum, as well as number of missing data (if relevant); while categorical variables will be presented as number of observations, count, percentage, and number of missing data (if relevant) in a frequency table. In general, missing values will remain as missing. Specific rules for handling missing efficacy data are described in Efficacy Analysis.

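### IOP is summarised by visit and by normal-range shift, with no any-visit count per subject, so transient or treated rises are understated though not hidden

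*Combined protocol and SAP*

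**What the plan says.** IOP is a listed safety measure in the synopsis. Its analysis is given only in the general wording of Safety Analysis:

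- IOP stands in one list with the physical examination, laboratory tests and other eye examinations, all to be described per arm.
- For continuous measures the rule is "Continuous safety data will be summarized by visit and include changes from baseline". General Statistical Considerations lists the statistics for continuous variables: "observations, mean, standard deviation, median, minimum, and maximum, as well as number of missing data (if relevant").
- For categories the rule is "Continuous data will also be converted to categorical values where possible (ie, below, within, and above normal ranges"), shown as shifts from baseline.
- For categorical results the display is "Categorical safety data collected by visit will be summarized showing the counts and percentages in each category at each visit", again with shifts from baseline.

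Safety Analysis also plans subject listings, per-group counts of subjects with each treatment-emergent adverse event (TEAE), and TEAEs by day of onset.

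Mm Hg limits for IOP appear only in the eligibility criteria. Exclusion 9 concerns an earlier pressure response to topical or systemic steroid: "a rise of ≥10 mm Hg or an absolute IOP ≥ 25 mm Hg which required treatment". Exclusion 11 bars "Active ocular hypertension (with or without treatment) ≥ 22 mm Hg in the study eye at the Screening or Day 1 visit". The synopsis gives no normal range for IOP, no worst post-dose value per subject, no any-visit threshold count and no summary of IOP-lowering treatment.

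**The concern.** The risk section of the synopsis names increased IOP among the expected reactions, and safety and tolerability of the different strengths is a secondary objective. The reader of the safety tables wants to know how many subjects in each group had a material rise, how large it was, and how many were treated for it. By-visit summaries answer a different question: what the group looked like on a given day.

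Three features make them understate a rise that is short or treated:

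- Rises at different visits fall in different tables, and nothing adds them up per subject.
- Once some subjects start IOP-lowering treatment, later visit means mix treated and untreated eyes.
- The above-normal category puts a small excess and a large one in the same cell.

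The efficacy side is better served. It has subject-level responder endpoints (a gain of at least 15 letters, CST below 300 µm) and explicit rules for data after rescue. IOP has no counterpart to either. Because the sponsor means to share key Part 1 results so that benefits and risks are understood, the two sides should be reported at a similar level of detail.

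**Working it through.** **Inputs.** The plan has no IOP figure to reproduce. Sample Size Calculation gives Part 1 groups of 10, 10 and 11 (10 + 10 + 11 = 31, as stated) and up to 30 subjects in Part 2. With 1:1 allocation that is up to 30/2 = 15 per group. Pooled Group 3 is up to 11 + 15 = 26. Visits 3 to 12 are 10 post-dose visits; I assume IOP is read at each.

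**1. Visit mean.** One subject with a rise of 10 mm Hg moves that visit's mean by 10/n:

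- n = 10: 1.0 mm Hg
- n = 11: 0.91 mm Hg
- n = 15: 0.67 mm Hg
- n = 26: 0.38 mm Hg

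**2. Visit proportion against any-visit proportion.** Suppose three of 15 subjects each have a rise at a different visit, back to baseline by the next.

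- Any-visit count: 3/15 = 20%. The exact (Clopper-Pearson) 95% interval runs from the 0.025 quantile of Beta(3, 13) to the 0.975 quantile of Beta(4, 12), which is 4.3% to 48.1%.
- Any one visit table: at most 1/15 = 6.7%.

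**3. Range over rates and timing.** The documents give no rate of IOP rise, so I simulated true any-visit rates of 10%, 20% and 30% with n = 15. Each affected subject has the rise at one visit only, chosen at random from all 10 visits or from just three. The average of the highest visit-level proportion was:

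| True any-visit rate | Spread over 10 visits | Clustered in 3 visits |
|---|---|---|
| 10% | 5.9% | 7.1% |
| 20% | 8.8% | 12.2% |
| 30% | 11.0% | 16.9% |

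Clustering reduces the gap but does not close it. Rises that last over several visits would reduce it further.

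**4. Shift table.** With an upper normal limit U, a rise of exactly 10 mm Hg stays within range when baseline is U − 10 or lower. The documents give no U. For U = 20, 21 or 22 the baseline limit is 10, 11 or 12 mm Hg. For U = 21, a rise from 11 to 21 is not shown as a shift, while 12 to 22 is. At the other end, 23 and 35 mm Hg share one cell. Because entry requires study-eye IOP below 22 mm Hg, a later reading of 25 or more would normally show as a new shift at its visit.

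**5. Precision of the proposed count.** With no subject affected, the exact upper 95% limit is 30.8% for 0/10 and 21.8% for 0/15.

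**The case against.** A reader might infer that the planned output hides IOP spikes. The documents do not support that. A rise read at a scheduled visit appears in that visit's maximum and maximum change, in the subject listings, and in the shift table if it crosses the limit. If it is reported as an adverse event, the TEAE table counts the subject once, whatever the visit. Treatment lowers later readings; it does not erase the one already recorded. In groups of 10 to 15, listings can be read line by line. This all stands, and it is why the right word is understate.

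Part of the gap remains. A visit maximum shows that at least one large value occurred, not how many subjects had one, and maxima cannot be added across visits. The TEAE count depends on what is reported, and the synopsis sets no IOP threshold for reporting. A rise seen only at an unscheduled visit could miss the by-visit tables. If the sponsor means the shift to run from baseline to the worst value, subjects above normal would be counted, but the text does not say so and the size of the excess would still be lost.

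A reader might also infer that exclusion 9 is a ready-made outcome definition. It is not. It concerns past response to topical or systemic steroid, and it is unclear whether its treatment qualifier covers both limbs. Its cut-offs can be borrowed, but that makes a new analysis definition.

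Finally, the study is exploratory, and Interim Analysis rules out formal comparisons between groups in either part. The proposed counts could not reliably establish a difference between strengths. That is a limit of size, not a reason to leave the counts out.

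**Conclusion.** The point holds as a low-cost improvement to safety reporting. As the synopsis stands, IOP gets by-visit descriptives and normal-range shifts, and subject-level counting rests on reported TEAEs. In the worked case the any-visit figure is 20% against at most 6.7% at any one visit. At a true rate of 20% the simulated highest visit proportion averages 8.8% to 12.2%, depending on clustering.

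These sizes rest on 15 subjects per group, on IOP being read at all 10 post-dose visits, and on each rise being seen at one visit only. The documents give none of the rates or durations, and longer rises would be diluted less.

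It would go too far to conclude that the plan would show a difference between strengths weakly or not at all: the maxima, listings and TEAE counts remain, and small groups limit any method. Nor do the documents describe the IOP risk as dose-related. The text reviewed is at synopsis level, so if a fuller safety section or a separate analysis plan already specifies such a table, the point is met.

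**What to change.** In Safety Analysis, add one descriptive study-eye IOP table by part and treatment group, with Group 3 also pooled as for efficacy, giving:

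- (a) each subject's maximum post-dose IOP and maximum change from baseline, including unscheduled readings, summarised by group;
- (b) the number and percentage of subjects with a rise of at least 10 mm Hg at any post-dose visit and, separately, with IOP of at least 25 mm Hg at any post-dose visit, stated to be analysis cut-offs adapted from exclusion 9;
- (c) the number of subjects starting IOP-lowering treatment, with visit summaries after such treatment flagged.

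Counting (b) and (c) separately avoids the unclear treatment qualifier in exclusion 9. The normal range used for the IOP shift tables should be stated, together with whether the shift is to each visit or to the worst value.

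The cost is minor programming for one more table from IOP data already collected. With 10 to 15 subjects per group the percentages are imprecise and should be presented as descriptive. Sample size, trial conduct and clinical management do not change.
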